Current therapy for indolent non-Hodgkin's lymphoma show high overall response rates but with some toxicity. A common regimen uses fludarabine, mitoxanterone, decadron and rituximab which produces over 90% overall response rate but with 20% prolonged bone marrow toxicity and myelodysplastic syndrome. To improve on these results, we plan to treat subjects with combination with rituximab which targets tumor cells and the immunomodulator analog lenalidomide that targets both the tumor cell and the cancer cell environment. This combination shows synergy in killing of lymphoma cells and minimal overlapping toxicity.

STUDY OBJECTIVES:

Primary:

To evaluate the overall response rate of lenalidomide in combination with rituximab in previously untreated indolent non-Hodgkin's lymphoma

Secondary:

To evaluate the toxicity of lenalidomide in combination with Rituximab in previously untreated indolent non-Hodgkin's lymphoma.

STUDY DESIGN: A open label Phase II single institution study of Lenalidomide in combination with rituximab in subjects with previously untreated indolent non-Hodgkin's lymphoma.

STUDY ENDPOINTS

Primary: To determine the number of CR, PR, and progression-free survival.

Secondary: Determine the type, frequency, severity, and relationship of adverse events to lenalidomide and rituximab.

STUDY DURATION: 1 year	TOTAL SAMPLE SIZE: 155
DOSING REGIMEN(S):	STUDY DRUG SUPPLIES:
Schedule A: Lenalidomide 20 mg po daily, with escalation up to 25 mg on days 1-21 of 28 day cycle for patients with follicular and marginal zone lymphoma. Rituximab 375mg/m2 IV x1 on day 1 of every cycle Total 6 cycles. -and- Lenalidomide 10 mg po daily, with escalation up to 25 mg on days 1-21 of 28 day cycle for patients with a diagnosis of small lymphomocyctic lymphoma. Rituximab 375mg/m2 IV x1 on day 1 of every cycle Total 6	For study participants, Celgene Corporation will provide lenalidomide at no charge through the RevAssist® program.

cycles.

Patients with evidence of tumor response after 6 cycles can remain on treatment for a total of 12 months.

Schedule B:

Lenalidomide 20 mg po daily, with escalation up to 25 mg on days 2-22 of 28 day cycle for patients with follicular lymphoma for cycles 1-6. Lenalidomide 10mg po daily for days 2-22 for cycles 7-12. Rituximab 375mg/m2 IV x1 on day 1,8,15 and 22 of cycle 1 and on day 1 of every subsequent cycle. Total 12 cycles. -and-

Lenalidomide 10 mg po daily, with escalation up to 25 mg on days 2-22 of 28 day cycle for patients with small lymphocytic lymphoma for cycles 1-6. Lenalidomide 10mg po daily for days 2-22 for cycles 7-12. Rituximab 375mg/m2 IV x1 on day 1,8,15 and 22 of cycle 1 and on day 1 of every subsequent cycle. Total 12 cycles.

Confidential

2. Schedule of Study Assessments

Procedure 8*	Screening < 30days from Baseline (First day study drug		Cycle 1	_		All Cycles	After Cycles 3, 6, 9,12	Discontinuation From Study Drug	Follow-Up Phase
	administration)	Day	Day	Day	Day	Day	Day		Every 3 ⁶
		-	ω	15	22	-	-		months
Record prior medications, treatments	×								
Record prior anti-cancer therapies	×								
HIV and Hepatitis B/C screening	×								
Physical examination, vital signs, weight	×					×		×	
ECOG performance status	×					×		×	
CT of the chest & abdomen / pelvis, neck, PET CT.	×						×	×	₉ ×
Chest x-ray	×						×	×	
Bilateral bone marrow Bx, BM cytogenetics. On Follicular lymphoma histology do BM and blood PCR for Bcl-2 rearrangement. On SLL/CLL do ZAP70, CD38 staining and somatic mutation analysis on BM and tumor tissue.	X ₂						X ₂	X_2^2	
Register patient into RevAssist [®] program ¹	×								
Prescribe lenalidomide via RevAssist® 1	×					×			
Rituximab infusion ¹²		*×	×	×	×	*×			
Hematology Test: hematocrit, platelet count, WBC count with differential, Absolute neutrophil count (ANC) and absolute lymphocyte count (ALC). 9, 11	×		×		×	×		×	

Page 8 of 50

Serum chemistry: Blood chemistries should include sodium, potassium, chloride, CO2, blood urea nitrogen (BUN), creatinine, glucose, aspartate aminotransferase (AST), alanine aminotransferase (ALT), total bilirubin, alkaline phosphatase, lactate dehydrogenase (LDH), calcium, phosphorus, and magnesium.	×		×		×	×		×	
Pregnancy test 3,4	*X	×	×	×	×	×		*X	
Tumor lesions assessment	×						×	×	
Response assessment using IWG criteria							×	×	
Record adverse events		×	×	×	×	×		×	
Record concomitant therapies/procedures						×		×	
Obtain Follow-Up anti-cancer treatments									₉ ×
Obtain Follow-Up survival information									₉ ×
Immune Studies 13		×				×			

^{*} Variations of +/- 3 days of the schedule are permitted

¹ Lenalidomide must be prescribed through and in compliance with Celgene's RevAssist® program. Prescriptions must be filled within 7 days.

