grade 4 hematologic toxicity. Seven evaluable (4 patients at 10 mg and 3 at 15 mg). Median age was 73, range 56-84; median prior lines of therapy were 3, range 1-4. Each cohort has 3 patients. No DLT has been encountered with a maximum Lenalidomide dose up to 20 mg. The number of cycles given ranged from 1 to 5 cycles. There were no grade 3 or 4 toxicities during cycle 1. Grade 1 non-hematologic toxic events included fatigue in 4, stomatitis in 3, pruritis in 3, and myalgias in 2. There was 1 episode of grade 2 anemia. The MTD has not been reached. Two patients had stable disease at cycle 3 and cycle 5, respectively. Four patients had progressive disease and were taken off the study. The combination provided stable disease in an aggressive lymphoma subtype with minimal toxicity. (22)

Preliminary results from this study have shown favorable response rates. In the first 13 patients evaluable for response, the overall response rate has been 85% with a complete response rate of 77%. The complete and overall response rate in patients with follicular lymphoma (n=7) has been 100%.

INDICATIONS AND USAGE:

Revlimid[®] (lenalidomide) is indicated for the treatment of patients with transfusion-dependent anemia due to Low- or Intermediate-1-risk myelodysplastic syndromes associated with a deletion 5q cytogenetic abnormality with or without additional cytogenetic abnormalities. Revlimid® is also approved in combination with dexamethasone for the treatment of patients with multiple myeloma that have received at least one prior therapy.

Adverse Events

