Schedule A: Lenalidomide will be administered orally at 20 mg total daily dose on days 1 to 21 of a 28 day cycle in patients with follicular and marginal zone lymphoma. Following cycle 3, if patients fail to show a response (partial or complete) the dose will be increased to 25mg/day. Patients with a diagnosis of small lymphocytic lymphoma (SLL) will begin at a dose of 10 mg total daily on days 1 to 21 of a 28 day cycle. This dose will be escalated by 5mg every 28 days up to 20mg if no toxicity is encountered. If no response is observed by cycle 3, the dose will be increased to 25 mg. (see dose modification for lenalidomide table). A single 375 mg/m2 intravenous dose of rituximab will be given at day 1 of every cycle.

Schedule B: Lenalidomide will be administered orally at 20 mg total daily dose on days 2 to 22 of a 28 day cycle in patients with follicular lymphoma. Following cycle 3, if patients fail to show a response (partial or complete) the dose will be increased to

25mg/day. Patients with a diagnosis of small lymphocytic lymphoma (SLL) will begin at a dose of 10 mg total daily on days 2 to 22 of a 28 day cycle. This dose will be escalated by 5mg every 28 days up to 20mg if no toxicity is encountered. If no response is observed by cycle 3, the dose will be increased to 25 mg. (see dose modification for lenalidomide table). A single 375 mg/m2 intravenous dose of rituximab will be given at day 1, 8,15, and 22 of cycle 1 and on day 1 of every subsequent cycle. In the absence of progression or toxicity, patients will remain on treatment for a total of 12 months. If patients attain a complete response following cycle 6 or 9, lenalidomide will be reduced to 10mg daily for the remaining cycles with the same dosing schedule of rituximab and lenalidomide as described above."

Patients that have documented clinical benefit and no evidence of progression of disease can remain on treatment for a total of 12 months. Treatment will be continued at the cycle 6 dose level with the same dosing schedule of rituximab and lenalidomide as described above.

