Several phase II studies have shown activity with lenalidomide in CLL. Higher doses (25mg) have been associated with increased toxicity in the form of an increased incidence of tumor flare and tumor lysis syndrome (TLS).27,28 Tumor flare has also been correlated with response and may be associated with lenalidomide efficacy. 29 However, lower doses (10mg) appear to be better tolerated and have been associated with fewer cases of tumor flare. Ferrajoli et al treated 35 patients with CLL with a starting dose of 10mg daily for 28 days with a dose escalation to 25mg as tolerated. There were no cases of tumor lysis reported, and only 12% of patients developed tumor flare. The median dose level was 10mg. 30 In another phase II trial with lenalidomide in CLL, 2 out of the first 25 patients experienced TLS at the initial starting dose level (25mg). The study was modified to begin at a lower starting dose and none of the 16 patients who started on the 10mg dose level experienced tumor lysis. The incidence of tumor flare was unchanged, but the severity of reactions decreased significantly.31

Response to therapy will be assessed after 3 cycles and after 6 cycles of chemotherapy. In patients that continue on with extended dosing beyond cycle 6, response will also be evaluated after 9 and 12 cycles of chemotherapy. If after 3 cycles of therapy, there is stable disease without progression, as defined by IWG criteria, the lenalidomide dose will be increased for a total daily dose of 25mg, or 5 mg above the current dose in patients with SLL. If there is evidence of progression of disease, the patient will discontinue study medication.

The rationale for schedule B is derived from studies in both CLL and multiple myeloma suggest a clinical benefit (response rate and PFS) with extended dosing of lenalidomide. In schedule B, the dose of lenalidomide will be reduced in responding patients on cycles 7-12 to minimize potential myelosupression with increased exposure. In addition, significant infusion reactions to rituximab have been noted to occur beyond cycle 2. Although etiology of the infusion reactions is unknown, the severity of the reaction may be potentiated by concurrent dosing of lenalidomide. Ancedotal experience suggests that starting lenalidomide on day 2 of treatment (rituximab on day 1) may lessen the observed toxicity. Dose intensification of rituximab (weekly dosing) will occur in cycle 1 to increase mean serum concentration early in treatment.

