Allergic reaction or hypersensitivity Grade 2-3	 Hold (interrupt) dose. Follow at least weekly. If the toxicity resolves to ≤ grade 1 prior to Day 21 restart at next lower dose level and continue the cycle until Day 21. 	Omit lenalidomide for the remainder of the cycle.
Grade 4	Discontinue lenalidomide study drug.	Discontinue lenalidomide study drug

Table 2: Dose Modification	n for Lenalidomide	
NCI CTC Toxicity Grade	Day 2-14 of Cycle	≥Day 15 of Cycle
Venous thrombosis/embolism ≥ Grade 3	 Hold (interrupt) dose and start anticoagulation; restart at investigator's discretion (maintain dose level). 	Omit lenalidomide for remainder of cycle. Anticoagulation measures as described in Conncomitant therapy section below.
other non-hematologic toxicity assessed as Lenalidomide-related ≥ Grade 3	 Hold (interrupt) dose. Follow at least weekly. If the toxicity resolves to ≤ grade 2 prior to Day 21 restart at next lower dose level and continue the cycle until Day 21. 	Omit lenalidomide for remainder of cycle.
Hyperthyroidism or hypothyroidism	Omit lenalidomide for remainder of cycle, evaluate etiology, and initiate appropriate therapy. Restart lenalidomide next cycle (decrease dose by one dose level).	Omit lenalidomide for remainder of cycle, evaluate etiology, and initiate appropriate therapy. Restart lenalidomide next cycle (decrease dose by one dose level).

[†] If patient had low baseline platelets due to prior to study entry, dose reduction not required.

Dose Escalation

In schedule B, all patients in a complete response will reduce lenalidomide to 10mg daily on cycles 7-12.

If after 3 cycles of therapy, there is stable disease without evidence of progression as defined by IWG criteria, the lenalidomide dose will be increased to 25 mg per day (dose level +1) or 5 mg above the current dose in patients with SLL. The initiation of the next cycle will only be initiated if there is no evidence of toxicity as outlined above in the Instructions for Initiation of a New Cycle.

Treatment compliance

Subjects will be asked to maintain a diary to record the drug administration.

Prohibited concomitant therapy

Concomitant use of sargramostim (GM-CSF), other anti-cancer therapies, including radiation, thalidomide, or other investigational agents is not permitted while subjects are receiving study drug during the treatment phase of the study.

Discontinuation of Study Treatment

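### Dosing rules conflict: Schedule B lenalidomide in cycles 7-12 has three versions, and SLL escalation after cycle 3 has two that differ below 20 mg

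*Combined protocol and SAP*

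**What the plan says.** **Schedule B, cycles 7-12.** The synopsis (Dosing regimen, Schedule B) says for follicular lymphoma "Lenalidomide 10mg po daily for days 2-22 for cycles 7-12" and repeats this for SLL: "small lymphocytic lymphoma for cycles 1-6. Lenalidomide 10mg po daily for days 2-22 for cycles 7-12". Neither entry depends on response.

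Section 5 does make the reduction depend on response. Overall design and Drug Administration both say "If patients attain a complete response following cycle 6 or 9, lenalidomide will be reduced to 10mg daily for the remaining cycles". Dose Escalation says "In schedule B, all patients in a complete response will reduce lenalidomide to 10mg daily on cycles 7-12". The rationale paragraph in Overall design uses a wider term: "In schedule B, the dose of lenalidomide will be reduced in responding patients on cycles 7-12".

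The paragraph in Overall design on patients with clinical benefit and no progression adds "Treatment will be continued at the cycle 6 dose level", but names no schedule.

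**SLL, no response after cycle 3.** SLL patients start at 10 mg and rise by 5 mg per cycle to 20 mg if there is no toxicity. For those without a response by cycle 3, the SLL sentences in Overall design and Drug Administration set the dose to 25 mg. The response-assessment paragraph of Overall design and the Dose Escalation section instead add 5 mg to the current dose for SLL patients with stable disease.

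**The concern.** Two prescribers can each follow the protocol and order different doses for the same patient.

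In the first conflict, the late-cycle reduction is a defining feature of Schedule B. The protocol justifies that schedule by extended dosing, with a lower dose late on to limit myelosuppression. If the synopsis is followed for some patients and Section 5 for others, Schedule B is not one regimen in cycles 7-12. Exposure, late adverse events, later response and progression-free survival would then be read over a mixture. (Progression-free survival is listed as primary in the synopsis but not in Section 4.)

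The second conflict is a safety matter. The ramp to 20 mg proceeds only without toxicity, so SLL patients below 20 mg at the end of cycle 3 are mainly those who were held or reduced. Overall design itself notes that 25 mg was linked to more tumor flare and tumor lysis in CLL and that 10 mg was better tolerated.

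**Working it through.** No figure in the plan is in dispute. The check sets the dosing statements side by side and works out the doses that follow.

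**1. Schedule B, cycles 7-12, by response status after cycle 6**

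| Status | Synopsis | Rationale paragraph | Overall design, Drug Administration, Dose Escalation |
|---|---|---|---|
| Complete response | 10 mg | reduced (dose not given) | 10 mg |
| Partial response | 10 mg | reduced (dose not given) | not reduced |
| Stable disease | 10 mg | not reduced | not reduced |

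The three sources agree only for complete response. Timing can differ as well: for a complete response first reached after cycle 9, the synopsis gives 10 mg from cycle 7, while Overall design and Drug Administration reduce only for the cycles that remain.

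Inputs: days 2-22 are 21 dosing days per cycle, and cycles 7-12 are six cycles, so 21 x 6 = 126 days. Total dose = daily dose x 126, assuming no interruptions.

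| Dose at cycle 6 | Synopsis | If continued | Ratio |
|---|---|---|---|
| 25 mg | 1,260 mg | 25 x 126 = 3,150 mg | 2.5 |
| 20 mg | 1,260 mg | 20 x 126 = 2,520 mg | 2.0 |
| 15 mg | 1,260 mg | 15 x 126 = 1,890 mg | 1.5 |
| 10 mg | 1,260 mg | 10 x 126 = 1,260 mg | 1.0 |

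**2. SLL without response after cycle 3**

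Inputs: the levels in the SLL dose adjustment table (level -1 is 5 mg, starting dose 10 mg, +1 is 15 mg, +2 is 20 mg, +3 is 25 mg, each for 21 days).

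| Current dose | Set to 25 mg | Add 5 mg | Per-cycle total (x 21) | Ratio | Levels climbed under the 25 mg rule |
|---|---|---|---|---|---|
| 20 mg | 25 mg | 25 mg | 525 v 525 mg | 1.00 | 1 |
| 15 mg | 25 mg | 20 mg | 525 v 420 mg | 1.25 | 2 |
| 10 mg | 25 mg | 15 mg | 525 v 315 mg | 1.67 | 3 |
| 5 mg | 25 mg | 10 mg | 525 v 210 mg | 2.50 | 4 |

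**3. Does other text settle either conflict?** No precedence rule is stated. The criteria for starting a new cycle require that counts and toxicity have recovered to set levels; once they have, nothing there limits the size of the step. The rule that carries a reduced dose into the next cycle does not say how it combines with escalation for lack of response.

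**4. Does either conflict reach the monitoring design?** Section 10 assesses toxicity at the end of cycle 1 and overall response at the end of cycle 3. Both conflicts begin later.

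**The case against.** The strongest reply to the first conflict is that a synopsis is a compression. It also omits the cycle-3 trigger for escalation, the rationale paragraph is not a dosing instruction, and the three operative statements in Section 5 agree. A prescriber working from those has one answer on when to reduce. This makes the complete-response rule the likelier intention and the natural target for the fix. It does not remove the conflict: the synopsis states the unconditional dose twice, as a specific instruction. Nor does Section 5 say outright what Schedule B patients not in complete response receive, because the sentence on continuing the cycle 6 dose names no schedule and resembles the extension offered under Schedule A.

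On the second conflict, the 25 mg sentence directly follows the ramp to 20 mg, the synopsis treats 25 mg as a ceiling, and the sentence points to the dose modification table. The authors probably had in mind a patient already at 20 mg. That stands. A reader might infer that the protocol intends to take a toxicity-reduced patient from 5 or 10 mg straight to 25 mg; no text says so. The sentence only permits that reading by leaving out the current dose.

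A reader might also apply the 2- to 2.5-fold range to every affected patient. It applies only from 20 or 25 mg. SLL patients start at 10 mg, and in the cited CLL study with a 10 mg start and escalation as tolerated, the median dose level was 10 mg. An SLL patient still at 10 mg receives the same dose under either rule.

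**Conclusion.** Both inconsistencies are real, stand in current operative text, and should be corrected. In cycles 7-12 a Schedule B patient in partial response or stable disease is assigned doses that differ 2- to 2.5-fold from 20 or 25 mg, 1.5-fold from 15 mg, and not at all from 10 mg. For SLL after cycle 3 the rules agree at 20 mg and give 25 against 20, 15 or 10 mg from 15, 10 or 5 mg. These sizes assume full 21-day dosing.

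The number of patients affected cannot usefully be estimated. It is tempting to use the preliminary results in Section 3: a 77% complete response rate in 13 patients is 10, and all 7 follicular patients responded completely, which leaves 3 of 6 in other histologies. Applying that half to the 15 SLL patients planned for Schedule B gives 7 or 8 not in complete response. The documents do not support the step. The six may include marginal zone patients, who are not treated on Schedule B, and the exact 95% interval for 3 of 6 is 12% to 88%, or about 2 to 13 of 15. The number of SLL patients below 20 mg after cycle 3 cannot be derived at all.

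Nor should a reader infer that the trial's decision rules are compromised. Stopping boundaries, sample size and the cycle-3 response assessment are unaffected. What is affected is dosing after cycle 3, patient safety in SLL, and the interpretation of later outcomes.

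**What to change.** **Schedule B, cycles 7-12.** Amend both synopsis entries and the rationale sentence to the rule in Overall design, Drug Administration and Dose Escalation: reduce to 10 mg only after a complete response at cycle 6 or 9. State explicitly that Schedule B patients not in complete response continue their current dose. If 10 mg for everyone is what the sponsor intends, change those three Section 5 statements instead.

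**SLL after cycle 3.** Amend the SLL sentences in Overall design and Drug Administration to the rule already in the response-assessment paragraph and Dose Escalation: 5 mg above the current dose, to a maximum of 25 mg.

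Two additions are for the sponsor to decide, since they would be new dosing rules. One is to keep a patient already below 10 mg at that dose at cycle 7, rather than raise it to the synopsis figure. The other is to step by table level from level -2 (5 mg for 14 days), where adding 5 mg would skip level -1 (5 mg for 21 days).

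The cost is one clarifying amendment to a few sentences, with the company review and ethics approval that Section 8 requires. It needs no new procedures, data, analyses or patients.

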Clinical experience in solid tumors with lenalidomide

Twenty patients with varying types of solid tumors (13 with malignant melanoma, 2 each with carcinoma of the pancreas and non-small-cell lung cancer [NSCLC], 1 each with renal carcinoma, breast carcinoma, and carcinoid-unknown primary) were enrolled in a Phase 1 study of lenalidomide conducted at the St. George Hospital, London, UK. This was a non-randomized, open-label with-in patient dose-escalation design, where patients started on 5 mg/day for 7 days and then increased their dose every 7 days to 10 mg/day, 25 mg/day, and 50 mg/day for a total of 4 weeks on therapy. ⁽⁶⁾

Investigators at the NCI have enrolled 20 patients, including 18 patients with recurrent high-grade gliomas and 2 with other refractory CNS malignancies (1 recurrent atypical meningioma and 1 multiple recurrent spinal hemangioblastomas) into a phase I trial of lenalidomide given on Days 1 through 21 every 28 days. Treatment has been well tolerated with 1 grade 2 myelosuppression as the only toxicity > grade 1. (7)

In an ongoing phase I trial in patients with refractory metastatic cancer conducted through the NCI, 12 patients with metastatic androgen independent prostate cancer have been enrolled. Lenalidomide was administered in daily doses of 5mg (3 patients), 10mg (3 patients) and 20mg (6 patients). Dose limiting toxicity was seen at 20mg/day (1 grade 3 thrombosis and 1 grade 3 hypotension). Stable PSA values for at least 8 weeks were observed in 6 patients. (8)

In a phase III, multi-center, randomized parallel group study comparing two dose regimens of lenalidomide, 293 patients with malignant melanoma were enrolled. Subjects were randomized to receive treatment with lenalidomide at a dose of 5 mg per day orally for 28 days or to 25 mg per day orally for 21 days with a 7 day rest (28 day cycle). Treatment continued until the patient developed disease progression or intolerable adverse events occurred. Interim analysis failed to show an advantage of one regimen over the other with respect to survival. Analyses of response rates are pending. The toxicity profile was similar in both dose groups and the most frequent adverse events were fatigue, seen in 32% of patients, followed by nausea and diarrhea, seen in 24% and 20% of patients respectively. Neutropenia and thrombocytopenia were seen in 2.4% and 2.0% of patients respectively. Grade 3 and 4 toxicities were seen infrequently (<15%).

A second phase III randomized trial compared a lenalidomide dose of 25 mg daily orally for 21 days with a 7 day rest (28 day cycle) to placebo in patients with metastatic melanoma. Three hundred and five patients enrolled on this study and a preplanned interim analysis failed to demonstrate a survival advantage. Response rates are being analyzed. The toxicity profile was favorable and similar to the previous phase III study. (16)

Clinical experience in multiple myeloma with lenalidomide

In 2 phase I studies in multiple myeloma, a total of 41 patients have been treated with lenalidomide. In one study at the University of Arkansas, 15 patients who relapsed or were refractory to high dose melphalan therapy with stem cell transplant were treated for 4 weeks in an open-label safety study and were permitted to continue therapy in an extension phase of the trial. Patient cohorts were treated at the following daily doses: 5mg, 10mg, 25mg, and 50mg. ⁽⁹⁾ In a similar study at the Dana Farber Cancer Institute, 27 patients with rapidly advancing refractory multiple myeloma were enrolled. ⁽¹¹⁾

Anti-mutliple myeloma activity was observed in each of these 2 phase I studies. Decreases in neutrophil and platelet counts were the dose-limiting toxicities associated with lenalidomide. The maximum tolerated dose (MTD) was not reached within 28 days. Due to dose modifications associated with myelosuppression observed beyond Day 28 at the 25mg and 50mg daily dose levels, the dose schedule most widely used in future studies has been lenalidomide 25 mg on Days 1-21, repeated every 28 days.

Pharmacokinetic analyses were performed on 15 multiple myeloma patients treated in the phase I studies. Absorption was found to be rapid on both Day 1 and Day 28 with time to maximum blood levels ranging from 0.7 to 2.0 hours at all dose levels (5mg, 10mg, 25mg, and 50mg). Plasma lenalidomide declined in a monophasic manner with elimination half-life ranging from 2.8 to 6.1 hours on both Day 1 and 28 at all 4 doses. No plasma accumulation was observed with multiple daily dosing. Peak and overall plasma concentrations were dose proportional over the dosing range of 5mg to 50mg. (12)

A multicenter, randomized, phase II trial compared 2 syncopated dose schedules of lenalidomide used alone or in combination with dexamethasone in the treatment of relapsed or refractory multiple myeloma. All patients were treated on Days 1-21 of a 28-day cycle. Patients treated with 15mg BID experienced more myelosuppression and dose reductions compared with patients treated with 30mg daily. Anti-myeloma activity was observed with each dose and schedule of single agent lenalidomide. The addition of dexamethasone to lenalidomide yielded responses in some patients who had not responded to lenalidomide alone. (13)

A recent phase II trial utilizing lenalidomide plus dexamethasone for newly diagnosed multiple myeloma patients was recently reported by the Mayo Clinic. Lenalidomide was given orally 25 mg daily on days 1-21 of a 28-day cycle. Dexamethasone was given orally 40 mg daily on days 1-4, 9-12, 17-20 of each cycle. Objective response was defined as a decrease in serum monoclonal protein by 50% or greater and a decrease in urine M protein by at least 90% or to a level less than 200 mg/24 hours, confirmed by two consecutive determinations at least 4 weeks apart. Thirty-one of 34 patients achieved an objective response, including 2 (6%) achieving complete response (CR), and 11 (32%) meeting criteria for both very good partial response and near complete response, resulting in an overall objective response rate of 91%. Of the 3 remaining patients not achieving an objective response, two had minor response (MR) and one stable disease. Forty-seven percent of patients experienced grade 3 or higher non-hematologic toxicity, most commonly fatigue (15%), muscle weakness (6%), anxiety (6%), pneumonitis (6%) and rash (6%). Rev/Dex is a highly active regimen with manageable side-effects in the treatment of newly diagnosed myeloma. (14)

A phase I/II trial of Liposomal doxorubicin (Doxil®), vincristine, dexamethasone (DVd) and lenalidomide in heavily pretreated relapsed/refractory multiple myeloma patients is ongoing. The MTD of lenalidomide was 10mg on Days 1-21 in combination with Doxil® 40mg/m2 IVPB on Day 1, vincristine 2mg IVP on Day 1 and dexamethasone 40mg PO on Days 1-4 cycled every 28 days. All patients received amoxicillin, acyclovir and aspirin 81mg prophylactically. The dose limiting toxicity with lenalidomide 15mg on Days 1-21 in combination with DVd was sepsis/septic shock. Additional phase I trials of lenalidomide with chemotherapy in advanced malignancies are in progress.

Celgene Corporation sponsored 2 multicenter, randomized, double-blinded, placebocontrolled phase III trials [1 U.S. (MM-009) and 1 international (MM-010)] in patients with relapsed or refractory multiple myeloma. (16) More than 350 patients were enrolled into each of these studies. All patients had to be considered sensitive to dexamethasone and were treated with dexamethasone 40mg qd, Days 1-4, 9-12 and 17-20. In addition to receiving dexamethasone, patients were randomized to lenalidomide 25mg qd or placebo, Days 1-21. Cycles were repeated every 28 days. After 4 cycles, there was a predetermined reduction of the dexamethasone dose to 40mg qd, Days 1-4 repeated every 28 days. In both studies, a pre-specified interim analysis conducted by an Independent Data Monitoring Committee demonstrated that subjects receiving the combination of lenalidomide (Len) plus dexamethasone (Dex) had significantly longer times to progression and higher response rates than those treated with single-agent dexamethasone. These studies led to the FDA approval of lenalidomide in combination with dexamethasone for the treatment of multiple myeloma in patients that have received at least one prior therapy.

Clinical experience in myelodysplastic syndromes (MDS), chronic lymphocytic leukemia and lymphoma with lenalidomide

An exploratory trial in 43 MDS patients with transfusion dependent or symptomatic anemia was conducted at the University of Arizona. (19) Patients received lenalidomide at doses of 25mg or 10mg per day, or of 10mg on Days 1-21, repeated every 28 days. All patients had had no response to erythropoietin or had a high endogenous erythropoietin level. Response rates were similar across the 3 dose schedules used. Responses were observed in 24 patients overall (56%) including 21 patients with a major response and 20 patients with sustained transfusion independence. Patients with a major response reached a median hemoglobin level of 13.2 grams per deciliter, with a corresponding 5.3 grams per deciliter median increase from baseline. After a median follow-up of 81 weeks, the median duration of major response had not been reached and was more than 48 weeks. Of 20 patients with karyotypic abnormalities, 10 (50%) patients had a complete cytogenetic remission. The response rate was highest in patients with a clonal interstitial deletion involving chromosome 5q31.1 (10 out of 12, 83%). Neutropenia and thrombocytopenia were the most common adverse events, and resulted in dose delays or reductions in 25 patients (58%).

Celgene Corporation sponsored a multicenter trial (MDS-003) of 148 MDS patients with a clonal interstitial deletion involving chromosome 5q31.1. Lenalidomide was given at a dose of 10mg on Days 1-21, repeated every 28 days, to 44 patients, and at a dose of 10mg daily to the other 104 patients. Transfusion independence was achieved in 93 patients (64%), with a median hemoglobin increase of 3.9g/dl. Cytogenetic response was achieved in 76% of transfusion independent patients with 55% achieving a cytogenetic

complete response. Pathologic complete response was documented in 32 out of 110 (29%) evaluable patients. With a median follow-up of 9.3 months, the median response duration had not been reached. Neutropenia (39%) and thrombocytopenia (35%) were the most common adverse events requiring dose delays or reductions. (17)

Another Celgene sponsored trial (MDS-002) in patients with low to intermediate-1 risk MDS enrolled 215 patients, of whom, 166 were documented to have low to intermediate-1 risk MDS. Among the patients with documented low to intermediate-1 risk MDS, 84 patients (51%) responded to treatment. Transfusion independence was achieved in 54 patients (33%) and 30 patients (18%) achieved a minor response, defined as a 50% or greater decrease in blood transfusion requirement. The median duration of transfusion-independence was 41 weeks. The median baseline hemoglobin level was 8.0g/dl, which increased by 3.2g/dl in responding patients. Among 20 patients evaluable for cytogenetic response, 9 patients (45%) experienced a cytogenetic remission. (16)

Lenalidomide in CLL and lymphoma

In a multicenter phase II study of Lenalidomide in relapsed/refractory aggressive non-Hodgkin's lymphoma, subjects with at least 1 prior treatment regimen received 25 mg lenalidomide daily on Days 1-21 of a 28 day cycle for 52 weeks. Response and progression were evaluated using the IWLRC methodology. The median age of the 22 response-evaluable subjects was 65 (46-83) and 13 were female. Histology was diffuse large B-cell [DLBCL] (n=12) follicular center lymphoma grade 3 [FL] (n=13), mantle cell lymphoma [MCL] (n=5) and transformed [TSF] (n=2). Median time from diagnosis to lenalidomide monotherapy was 2.3 (0.7-7) years and median number of prior treatment regimens per subject was 2 (1-6). Seven subjects (32%) exhibited an objective response (2 complete responses unconfirmed (Cru) and 5 partial responses (PR)), 6 had stale disease (SD) for a tumor control rate (TCR) of 59%, and 9 progressive disease (PD). Responses were produced in each of the aggressive histologic subtypes studied: DLBCL (3/12), FL (1/3), MCL (2/5) and TSF (1/2). Grade 3 or 4 adverse events occurred in 18 of 31 (58%) subjects receiving drug. These were predominantly Grade 3 hematological events (neutropenia, thrombocytopenia) with only 4 subjects (13%) experiencing a Grade 4 adverse reaction. These preliminary results relapse/refractory aggressive NHL indicate that lenaliodomide monotherapy is active with manageable side effects. (19)

A. Ferrajoli, et. al., at MD Anderson in a phase II study at MD Anderson of CLL patients who had received at least one purine analog-based regimen, were given lenalidomide 10 mg daily for 28 days followed by titration upward by 5 mg increments every 28 days to a maximum dose of 25 mg daily. 22 patients have received treatment for at least 3 months and are therefore evaluable for response. The median age was 64 years (range 49-82) and

the median number of prior treatments was 4 (1-15). β 2m was 4.1 mg/dL (1.6-10.1). 12 patients (55%) had Rai stage III or IV disease. 8 patients (36%) were refractory to fludarabine and 7 patients (32%) to alkylating agents. Responses according to NCI-WG criteria assessed after 3 months of treatment showed that 7 patients (32%) achieved a response [1 CR (5%), 1 nodular PR (5%), 5 PR (23%)]. 9 patients (41%) attained stable disease or clinical improvement and are continuing on treatment, and 6 patients 27% progressed, including one early death that occurred on day 22 secondary to mucormycosis. Fatigue was reported in 59% (G3 in 5%), nausea in 45%, pruritus in 31% and diarrhea in 22% (G3 in 5%). Myelosuppression occurred in 55% of the patients (32%) \geq G3 neutropenia and/or thrombocytopenia). Infectious complications were observed in 6 patients. (20)

In a multicenter phase II study of lenalidomide in relapsed/refractory indolent non-Hodgkin's lymphoma T. Witzig, et al treat subjects with 25 mg lenalidomide daily on Days 1-21 every 28 days and continue therapy for 52 weeks. The median age of the 15 response-evaluable subjects was 64 (54-82) and 5 were female. Histology was small lymphocytic lymphoma (SLL) (n=8), follicular center lymphoma grades 1, 2 (FL) (n=5) and nodal marginal B-cell lymphoma (NML) (n=2). Median time from diagnosis to lenalidomide monotherapy was 7.6 (3-14) years and median number of prior treatment regimens per subject was 3 (1-17). Using the IWLRC methodology, two subjects (13%) exhibited an objective partial response (PR) at four months. Both responses, one FL and one NML, occurred in subjects with substantial tumor burden. The 4-month time-toresponse for these indolent NHL subjects was longer than the time-to-response in aggressive NHL subjects (n=7) following lenalidomide monotherapy. Seven patients had stable disease (SD) for a tumor control rate (TCR) of 60% and 6 had progressive disease (PD). Grade 3 or 4 adverse events occurred in 9 (39%) subjects. These were predominantly Grade 3 hematological events (neutropenia, thrombocytopenia) with only 3 subjects (13%) experiencing a Grade 4 adverse reaction (all neutropenia). Lenalidomide monotherapy in indolent NHL showed evidence of activity with an acceptable safety profile. (21)

Lenalidomide in combination therapy in lymphoma.

In a phase I/II study of Lenalidomide in combination with Rituximab in relapsed/refractory mantle cell lymphoma with 1-4 prior therapies, M. Wang, et.al., at MD Anderson, subjects were given Lenalidomide daily for 21 days followed by 7 days of rest and Rituximab 375 mg/m² weekly for 4 weeks. A standard phase I dose escalation was used to determine MTD with Lenalidomide dose levels at 10 mg, 15 mg, 20 mg, and 25 mg. Dose-limiting toxicity (DLT) was defined as grade 3 or 4 non-hematologic or

